The system consists of a gaze-based hyperacuity perimetry device that requires no physical interaction, the software generates proprietary metamorphopsia detection algorithms, and the specific telemonitoring protocols that are followed at a prescribing trial centre. Occutrack supplies the devices to patients who have received a prescription from an ophthalmologist.

OCCUTRACK

[figure not shown]

Figure 2 A: The device comprises of a proprietary camera that tracks the user's gaze point. B: Perspective of the camera machine vision augmentation.

[figure not shown]

Figure 3 Participants in the study will be provided with a monocular occluder that is attached to A: corrective prescription frames (a) or a B: lensless frame, gaze-tracking accuracy is unaffected by lenses.

When an wAMD patient takes a test done twice weekly — the results are transmitted electronically to the clinical trial site. If the algorithm detects suspicious results, a digital flag is raised and a manual comparison to the patient's baseline is reviewed by the principal investigator (PI).

As for test results, the location and size of metamorphopsias and scotomas are inferred from the patient's reaction patterns to a series of generated dot patterns that the CRYSTALSIGHT device flashes at various points in the visual field. Some dots appear, move and disappear pseudo-randomly on the screen, the patient simply needs to look at the screen.

The purpose of this clinical validation study is to demonstrate that the CRYSTALSIGHT automated vision screening device is suitable for use at home twice a week to detect the recurrence of wet AMD in all ethnic groups.

Compared with the patient's baseline tests, erroneous or absent clicks indicate metamorphopsia, which could be due to early choroidal neovascularization (CNV). The threshold for a positive test for each parameter before this study start is determined by the on-going cohort-1 clinical study in progress.

Patients are automatically reminded if they fail to test themselves regularly. The treating ophthalmologist receives monthly longitudinal reports and immediate

OCCUTRACK

notification of abnormal readings so that an examination can be scheduled immediately.

The patterns of the dots are described as follows:

Static Fixation Evaluation (SFE)	Static Perimetry Assessment (SPA)	Static Perimetry Sensitivity Assessment (SPSA)	Pursuit
Visual Field fixation	Saccadic visual field	Saccadic Visual Field Sensitivity	Ocular motility

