This study will use the CRYSTALSIGHT system in an unsupervised home setting. Participants will perform biweekly self-monitoring with the CRYSTALSIGHT device. The threshold algorithm will be implemented and validated with subjects. Threshold information from Cohort 1 will thus be incorporated into the Cohort 2 intervention measures. Figure 5 illustrates the function of the CRYSTALSIGHT score as the basis for an intervention measure: an earlier-than-expected clinic visit should be scheduled immediately for clinic vision testing and urgent anti-VEGF administration.

Pro Re Nata (PRN): Standard treatment (control arm)

Participants randomized to the standard treatment arm received specific instructions from investigators for self-monitoring of vision at home to detect progression of AMD. Aids such as the Amsler grid. This group is referred to below as the standard treatment group. If participants experienced symptoms, they were instructed to call their clinical centre immediately and schedule an appointment within 72 hours.

PRN+: Home monitoring device (device arm)

In addition to the same standard of care instructions, participants will receive a CRYSTALSIGHT home monitoring device with instructions for installation and use. This arm is referred to below as the device arm. In cases where baseline measurements could not be obtained due to a pre-existing visual field defect in at least one study eye, participants returned the device and continued monitoring with standard treatment only but were still included in the final analyzes in the intent-to-treat (ITT) cohort as part of the device arm.

Participants were encouraged to use the device twice a week, and results were automatically transmitted via internet cloud to a Occutrack's data monitoring center. If testing of the device indicated a change from baseline measurements, an alert was sent from the monitoring center to the participant's clinical center, prompting staff to schedule an appointment with the study ophthalmologist within 72 hours.

This study is an open-label, randomized study designed to evaluate the safety and efficacy of the CRYSTALSIGHT device when used by patients in their own homes. The study will

OCCUTRACK

recruit a group of patients who meet certain eligibility criteria and provide them with the CRYSTALSIGHT device for use at home.

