The Cohort 2 study typically several phases, including a screening phase to identify eligible patients who could be recruited patients exiting the anti-VEGF injection clinic. The phases are:

- **Training:** a training phase for the device to ensure that patients know how to use the device properly, a testing phase in which patients use the device to monitor their vision condition using the CRYSTALSIGHT device over a period of time until the device detects deterioration in vision and meets the criteria for deterioration established by the Cohort 1 results, and a follow-up phase to assess results and obtain feedback from patients.
- **Monitoring:** During the study, patients will be asked to follow the specific protocols and guidelines for use of the CRYSTALSIGHT device, such as completing the bi-weekly regular testing. Patients will also be asked to report or provide feedback on any adverse events or problems encountered while using the device.
- **Intervention:** Should the CRYSTALSIGHT device determine that a threshold for vision deterioration has been reached (delta deviation of 10 points from the nominal baseline), the patient/participant will receive a notification from the prescribing physician and the electronic alert system via email to the subject's personal mobile device instructing them to schedule an appointment for confirmation OCT -A that the subject's wet AMD has recurred, see Figure 6 below.

[figure not shown]

Figure 6 True-False confusion matrix of cohort-2 will require OCT confirmation of wet AMD disease recurrence that was detected by CRYSTALSIGHT.

This cohort 2 intervention study is designed to collect data on the safety and efficacy of the device, including information on the accuracy, reliability, and ease of use of the device. The study may also examine the impact of the device on patient outcomes, such as changes in visual status or quality of life.

Once the study is complete, the data will be analyzed to determine if the device is safe and effective for home use. If the results are positive, the device can be submitted to the FDA for approval and made available to patients who need it.

OCCUTRACK

Cohort-2 study relationship to the cohort-1

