- Maintenance Monitoring:** Once the participant has achieved a nominal baseline level of visual performance, the system will remind the participant to regularly monitor their visual performance with the CRYSTALSIGHT device at the scheduled frequency.

OCCUTRACK

6. **Follow-up:** The PI will schedule regular follow-up appointments to monitor the participant's progress and adjust monitoring frequency as needed.

It is important to note that CRYSTALSIGHT does not work for all participants and it may take several months to detect disease relapse.

Study Schedule Table

Baseline Visit #1 Month 1	
Standard Routine Care
 
 • Visual Acuity (VA) • BCVA (Optional) • Optical Coherence Tomography (OCT) • Colour Fundus Photography • Clinical Consultant Review • Intravitreal Injections (IVT) 
Research Procedure
 
 • CRYSTALSIGHT Eye Gaze Tracking for investigative arm and insurance of CRYSTALSIGHT device for home monitoring. 
OR
 
 • Amsler Grid for Amsler Grid arm
Follow Up Visit #2 Month 2 (+/- Four weeks)	
Standard Routine Care
 
 • Visual Acuity (VA) • BCVA (Optional) • Optical Coherence Tomography (OCT) • Colour Fundus Photography • Clinical Consultant Review • Intravitreal Injections (IVT) (Optional)
Follow Up Visit #3 Month 3 (+/- Four weeks)	
Standard Routine Care
 
 • Visual Acuity (VA) • BCVA (Optional) • Optical Coherence Tomography (OCT) • Colour Fundus Photography • Clinical Consultant Review • Intravitreal Injections (IVT) (Optional)
Follow Up Visit #4 Month 4 (+/- Four weeks)	
Standard Routine Care
 
 • Visual Acuity (VA) • BCVA (Optional) • Optical Coherence Tomography (OCT) • Colour Fundus Photography • Clinical Consultant Review • Intravitreal Injections (IVT) (Optional)

OCCUTRACK

Follow Up Visit #5 Month 5 (+/- Four weeks)	Standard Routine Care 
 • Visual Acuity (VA) • BCVA (Optional) • Optical Coherence Tomography (OCT) • Colour Fundus Photography • Clinical Consultant Review • Intravitreal Injections (IVT) (Optional)
Follow Up Visit #6 Month 6 (+/- Four weeks)	Standard Routine Care 
 • Visual Acuity (VA) • BCVA (Optional) • Optical Coherence Tomography (OCT) • Colour Fundus Photography • Clinical Consultant Review • Intravitreal Injections (IVT) (Optional)

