5. Subjects undergoing treatment for Wet-AMD without any signs and symptoms of recurrence of active AMD (AMD recurrence: choroidal neovascularisation,

OCCUTRACK

intraretinal or subretinal fluid is present) with OCT lesion fluid volume more than 2 mm² or ILM height more than 300µm.

6. Ability to comply with the study protocol, in the investigator's judgment.
7. Subjects must be able to understand and provide informed consent. A signed informed consent form must be provided before any study assessments.

Exclusion criteria

1. Unable to understand verbal spoken instructions and demonstrate device functionality and implementation.
2. Unable to turn on and connect the CRYSTALSIGHT device to a computer independently.
3. Any ocular surgery in the previous 3 months, or vitrectomy in the previous 12 months
4. Any history of macular pathology unrelated to AMD affecting vision or contributing to the presence of intraretinal or subretinal fluid in the study eye
5. Any concurrent intraocular condition in the study eye that, in the opinion of the investigator, could either reduce the potential for visual improvement or require medical or surgical intervention during the study
6. Any prior or concomitant treatment for CNV or vitreomacular-interface abnormalities in the study eye.
7. History of idiopathic or autoimmune-associated uveitis in either eye
8. Active ocular inflammation or suspected or active ocular or periocular infection in either eye.

Study population: patients with recurrent vision problems diagnosed with active Wet-AMD at TTSH eye clinics.

Pre-specified clinical outcome: The prespecified adverse clinical outcome used in this study will be the **recurrence of Active Wet AMD**, which will be identified by an increase in central retinal thickness (CRT) of at least 50 microns or a loss of best-corrected VA of 5 letters or more.

Training

To prepare for home use of the CRYSTALSIGHT device, the following processes are performed in the clinic:

- The examining physician or study coordinator will unpack a CRYSTALSIGHT training unit for the patient to help the patient understand the device and ensure that the home user understands the device, its purpose, and how it works. Instructions on how to set it up at home include connecting the device to a laptop with an Internet connection.

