4. Follow best practices: The participant should follow best practices when using the device, including placement, head position, and attention to stimulation targets on the screen.

By following these steps, a new user can master the CRYSTALSIGHT health monitoring device and effectively manage their AMD condition.

How are they going to get the device

One CRYSTALSIGHT boxed unit will be signed over to the study participant to bring home after the recruitment administration is done during the regular clinic check-up and when the participant has agreed and signed the Informed Consent Form (ICF) to be included in the study.

System reminders

A study coordinator will monitor the electronic records system and will call the participant to conduct a self-test at home if they miss the test by 1 day. A system

OCCUTRACK

reminder will automatically send a message and email to remind the user to take the test if a scheduled self-test is missed by a day.

Results and reporting: The results of the tests will be transmitted to a secure server where they will be analyzed by the principal investigator and study coordinator. If any changes in vision are detected, the subject will be contacted by the study coordinator and a follow-up appointment will be scheduled.

Sample size calculation:

According to the workflow, all participants will have routine visits to clinic with OCT scans performed once every 4 weeks. Participants randomised into the CRYSTALSIGHT group will have measurements taken twice a week if the testing results are all negative. In case of a positive result with CRYSTALSIGHT, another test will be done on the next day. Participants will be recalled for review after two consecutive positive results are presented. Depending on the pathology presented on the OCT scan, IVT may be given for disease management. On the other hand, participants randomised into the Amsler Grid group will be evaluated by Amsler Grid and by OCT.

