For participants in the CRYSTALSIGHT group, each participant will have a testing result by CRYSTALSIGHT and by OCT every 4 weeks or less if the positive result triggers a clinical visit. The result is considered correct if it is consistent with the findings of the OCT scan. During the one-year study period, the total number of correct results generated by CRYSTALSIGHT will be counted and the accuracy for these participants will be calculated as number of correct results divided by the total number of clinical visit. For participants in the Amsler Grid group, the accuracy for each participant will also be calculated.

According to literature, the accuracy of Amsler Grid in detecting disease activity was about 80%, we will assume that CRYSTALSIGHT has the same accuracy. For the Singapore population, we will also assume that standard deviation of the accuracy to be 0.12 and setting the maximum allowable difference in accuracy (non-inferiority margin) between the two groups to be 0.09, with one-sided type 1 error of 0.025 and a power of 0.8, a total of 52 participants will be required (26 per group). Considering of 15% attrition rate, a total of 60 participants will be required.

For global study, we assume a higher standard deviation of the accuracy to be 0.21 and a dropout rate of 21%, a total of 220 participants will be required (110 per group).

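### The exit rule, re-treatment and one-year accuracy counting are not reconciled and no post-treatment reference is named, so visits after a recurrence can enter the accuracy ratio differently in the two arms

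*Protocol*

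**What the plan says.** **Alerts.** The Intervention item of the study phases sets the trigger at a "delta deviation of 10 points from the nominal baseline". The PRN+ section uses the same kind of reference: "If testing of the device indicated a change from baseline measurements, an alert was sent from the monitoring center". The investigator's manual check of a flag, described under The Device, is also against baseline. Recruitment places the setting of that baseline in initial monitoring, with routine monitoring starting "Once the participant has achieved a nominal baseline level of visual performance". Nothing says which baseline applies after a treated recurrence.

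**Recurrence.** Under Eligibility it is an "increase in central retinal thickness (CRT) of at least 50 microns or a loss of best-corrected VA of 5 letters or more". The Primary Objective and Methodology use the same two criteria. None of the three says from which visit the change is measured.

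**Leaving or staying.** The Figure 5 caption has a participant exit once CRYSTALSIGHT has correctly detected a recurrence and OCT has confirmed it. The Training item of the study phases runs device testing until deterioration is detected, and the cohort comparison table lists intervention and then exit. Study Design, however, allows re-treatment after a recall. The sample size section says "IVT may be given for disease management", and the Study Schedule Table lists optional injections at Visits 2 to 9 and 12 (none at Visits 10 and 11).

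**Scoring.** "During the one-year study period, the total number of correct results generated by CRYSTALSIGHT will be counted". This count is divided by the number of clinic visits. A result is correct when it agrees with OCT. Accuracy is also to be calculated for each Amsler participant.

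**The concern.** The primary comparison is a mean of per-participant accuracy ratios, so which visits enter each ratio must be the same in both arms. Two features put that at risk.

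First, a participant who stays in after a treated recurrence may have a dry retina and a lasting scotoma or distortion. If the device score remains 10 points or more from a baseline set before the recurrence, the device stays positive. The next-day repeat test does not filter this out, because a stable deficit is positive twice. At each later visit with an inactive OCT the result is scored wrong, although the device is correctly reporting a change that has already been treated.

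Second, the only exit stated is tied to a correct device detection. If it is applied, the device arm loses post-recurrence visits that the Amsler arm keeps. If it is not applied, those visits stay in the device arm. The protocol supports either practice, and three sites could differ.

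At stake is whether a difference set against the 0.09 margin reflects detection or the handling of visits after treatment.

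**Working it through.** **1. The plan's own figure.** Inputs from the sample size section (global study): SD 0.21, margin 0.09, one-sided alpha 0.025, power 0.80, dropout 21%, equal true accuracy of 0.80.

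- n per group = 2 × (1.960 + 0.842)² × (0.21/0.09)² = 85.5, so 86.
- With dropout: 86/0.79 = 108.9, so 109 per group and 218 in total, against 220 stated. Reproduced.
- Standard error of the difference with 86 evaluable per group: 0.21 × √(2/86) = 0.0320.

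**2. One affected participant.** Visits 2 to 12 give 11 follow-up visits. Suppose a recurrence is treated at Month 4, and at all 8 later visits the device is positive and the OCT inactive. Accuracy is then (3 × 0.80 + 8 × 0)/11 = 0.218 instead of 0.80. This is the extreme case.

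**3. Arm level.** Let f be the share of device-arm participants who stay in with a lasting deficit, and s the share of their visits that follow the event. Then:

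- fall in mean accuracy = 0.80 × f × s
- power = Φ((0.09 − fall)/0.0320 − 1.960), with the Amsler arm unaffected

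The protocol gives neither f nor s. With s = 0.5:

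| f | Fall | Power |
|---|---|---|
| 0 | 0 | 80% |
| 5% | 0.02 | 59% |
| 10% | 0.04 | 34% |
| 20% | 0.08 | 5% |

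**4. Effect of the exit rule.** Assume 30% recur, 25% of those keep a deficit, and s = 0.5.

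- Everyone stays: f = 0.30 × 0.25 = 0.075, fall 0.03, power 47%.
- Correctly detected cases exit and 20% of recurrences stay: f = 0.075 × 0.20 = 0.015, fall 0.006, power 75%.

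**5. If Amsler results are affected too.** The between-arm shift is 0.80 × s × (f_device − f_Amsler).

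- Equal shares: the shift is zero.
- Exit applied in the device arm only, with Amsler participants affected as in the first case of step 4: 0.80 × 0.5 × (0.015 − 0.075) = −0.024. The shift is now in the device's favour, and 0.024/0.09 is 27% of the margin.

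So the same text allows a shift against the device or towards it, depending on who leaves and on how Amsler results behave.

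**The case against.** The strongest reply is that exit closes the main route. A device-detected, OCT-confirmed recurrence ends participation, so it leaves no later visits to mis-score. What remains are recurrences found by monthly OCT or by symptoms. In those the device raised no confirmed alert while disease was active, and it is not obvious why many would then sit 10 points off baseline once dry. This stands in part: step 4 shows that the loss is small if exit is applied. It does not settle the matter, because the re-treatment and one-year counting passages point the other way, and because an exit in one arm only creates its own imbalance.

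It can also be said that a lasting distortion may keep an Amsler grid positive. That stands. No post-treatment rule is given for Amsler either, so unequal impact is possible but not shown.

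A third reply is that choosing the visits for analysis is often left to an SAP. That is fair for the choice itself. The conflict over who leaves the study, and the missing reference visit in the outcome definition, are in the protocol text.

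A reader might infer more than the documents support:

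- *That recurrence is anchored to the entry value.* No reference visit is named.
- *That a lasting 5-letter loss would make later alerts automatically correct, raising accuracy.* The scoring sentence refers to OCT findings, not BCVA.
- *That every later visit is mis-scored.* This needs a lasting deficit past the threshold, an inactive OCT and continued participation.
- *That injections are possible at every visit.* Visits 10 and 11 list none.
- *That the arm mean shifts by more than the margin.* With 20% of the arm affected from Month 4, the shift is 0.20 × (0.218 − 0.80) = −0.116. Share, timing and full persistence are all assumed, and the Amsler effect is set to zero.

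**Conclusion.** The point holds in limited form. The protocol ties alerts to a single nominal baseline, names no reference visit for the CRT or BCVA change, and does not reconcile a device-only exit with re-treatment and a one-year count. As written, the accuracy ratio is not guaranteed to cover comparable visits in the two arms, and some post-treatment visits can be scored against the device for a deficit that is already known.

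The size is unknown, and so is the net direction. It depends on recurrence and lasting-deficit rates that the protocol does not give, on whether exit is applied, and on how far Amsler results are affected in the same way. The illustrations range from a fall of 0.006 with exit to 0.03 without it (Amsler unaffected), and to a shift of 0.024 in the device's favour if exit is applied in one arm only and Amsler is affected. None of these is an estimate for this trial. The matter should be settled before enrolment, since exits and live alerts cannot be undone in analysis.

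**What to change.** - Define each participant's primary accuracy from visits up to and including the first OCT-confirmed recurrence, by whatever route it was found and identically in both arms. Report later visits separately.
- Name the reference visit for the CRT and BCVA changes.
- Reconcile the exit statements (Figure 5 caption, study phases, cohort comparison table) with the re-treatment and one-year counting statements (Study Design, sample size section). State whether exit applies to the Amsler arm and to recurrences found by another route.
- State which baseline live alerts use after treatment. That is a clinical and operational decision for the sponsor and investigators, and no rule is proposed here.

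The cost is protocol wording, with no new visits or procedures. The downside is fewer scored visits for participants who recur: a first recurrence at Month 4 leaves 3 of 11 follow-up visits. Ratios built on few visits vary more, so the assumed SD of 0.21 should be checked against the truncated measure.

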To demonstrate that the home monitoring of a PRN regimen with the CRYSTALSIGHT telemonitoring system is non-inferior to the Amsler grid¹ in detecting recurrence of wet AMD based on central retinal thickness (CRT) increase of at least 50 microns or a loss of best-corrected visual acuity (BCVA) of 5 letters or more.

Detection of using visual field test gaze tracking results in earlier detection of AMD/DME associated with (CNV), as reflected by better visual acuity compared with standard care. Outcome of this trial is to determine the sensitivity and specificity of CRYSTALSIGHT with reactivation subtle neovascular age-related macular degeneration that was detected by the regular use of a home monitoring device based on gaze-based preferential hyperacuity visual field testing.

An important predictor of the benefit of treatment with anti-vascular endothelial growth factor (VEGF) agents is visual acuity at the time of CNV treatment.

Secondary Objectives

1. Correlate CRYSTALSIGHT scores with BCVA and OCT findings.
2. Identify diagnostic performance of CRYSTALSIGHT (ROC, AUC).
3. Develop risk scoring algorithms for wet AMD recurrence.

Background work

For patients who have lost vision in one eye due to wet age-related macular degeneration (wAMD), preservation of functional visual acuity in the other eye is of paramount importance. However, clinical experience and research have shown that these and other high-risk patients often fail to use the Amsler grid between clinic visits to detect the earliest signs of neovascularization in their good eye.

Normal human vision consists of a series of rapid eye movements called saccades that abruptly change the fixation point depending on the area of the person's eye. OCCUTRACK's CRYSTALSIGHT device tracks these eye movements with generated

OCCUTRACK

patterns on the screen, a visual assessment of affected and unaffected eyes is achieved without expensive optics and at home on any tablet or laptop computer.

CRYSTALSIGHT is a home-based gaze-tracking readily available for home hyperacuity monitoring for these and other high-risk eyes with diagnosed wet-AMD.

The Device

[figure not shown]

Figure 1 CRYSTALSIGHT device being used in a home-based setting.

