A single large discrete target is displayed filling the entirety of the screen and shrinks to 10pixels for 5 seconds. The target is presented twice. The user under test's fixation radius is scored as a Circular-Error Probable (CEP) size. The smaller the CEP radius, the better the test result.	A set of 13 discrete targets are displayed randomly and twice repeatedly on fixed coordinates for a preset duration of 1 second (adjustable) on the screen for the user under test. Targets are presented in a pseudo-randomly to avoid bias in gaze point detection. An area-of-effect radius is scored if the user's gaze intersects with the presented target.	A set of 13 discrete targets that increases in radius at 10 pixels/second are displayed randomly on fixed coordinates on the screen for the user under test. Targets are presented in a pseudo-randomly to avoid bias in gaze point detection. The target radius is scored if the user's gaze intersects with the presented target at the presented radius size. The smaller the radius, the better the test result.	Subject under test to pursue a generated target moving in a sinusoidal pattern at a speed of 5cm/s.

OCCUTRACK

Methodology

This study aims to determine whether home-based monitoring using the CRYSTALSIGHT gaze-based Hyperacuity Perimetry system, when added to a PRN treatment regimen, is non-inferior to standard care using the Amsler Grid in detecting recurrence of choroidal neovascularisation (CNV) associated with wet age-related macular degeneration (AMD).

Recurrence is defined by a central retinal thickness (CRT) increase of ≥ 50 microns or a loss of best-corrected visual acuity (BCVA) of ≥ 5 letters.

The study also aims to evaluate whether CRYSTALSIGHT enables earlier detection of CNV progression, as reflected by better VA and CRT values at the time of detection, through biweekly self-tests conducted in an unsupervised home setting.

Study Design

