This is a randomised, open-label, non-inferiority clinical trial comparing two parallel arms: a standard care arm using Amsler Grid home monitoring (PRN), and an intervention arm using the CRYSTALSIGHT gaze-tracking system (PRN+). A total of 220 (Singapore – 60, United Kingdom – 80, United States – 80) participants will be randomised in a 1:1 ratio. Participants in the intervention arm will self-administer biweekly CRYSTALSIGHT tests at home, while those in the control arm will use the Amsler Grid. Both arms will attend monthly clinic visits for standard evaluations, including VA, BCVA, and OCT. Alerts generated by the CRYSTALSIGHT system based on deviation thresholds will trigger early clinic recall for confirmatory imaging and potential re-treatment.

[figure not shown]

Figure 4 Details of the home-use clinical trial study design. The trial objective: show that PRN+ is non-inferior to standard of care PRN with better VA/VF outcomes

Development of CRYSTALSIGHT cutoff scores should have been conducted in the cohort-1 1 study [NCT: NCT06518512] (Analysis). This Phase 2 should be the application of validated cut-off scores. The second aim will be to compare the accuracy of CRYSTALSIGHT and Amsler, and sensitivity and specificity check.

In addition to identifying CRYSTALSIGHT visual risk prediction cut-off scores, detection yields, and diagnostic Performance indicators will also be evaluated. Progression to CNV was

OCCUTRACK

determined by the investigator, based on standardised OCT confirmation. At the clinical trial site, these events were confirmed by gradings conducted by masked, certified independent personnel who did not know the treatment assignment. Events from both arms are graded using a standardised protocol.

[figure not shown]

Figure 5 In Cohort 2, home-based score deviation detected, study coordinator will schedule hospital checkup immediately. If CRYSTALSIGHT correctly detects wet AMD recurrence confirmed by OCT, subject exits the study.

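### Recurrence is defined by CRT or BCVA, but the schedule makes BCVA optional at all 12 visits and the only endpoint with a margin is scored against OCT alone

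*Protocol*

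**What the plan says.** **Definition.** The Primary Objective bases recurrence on a "central retinal thickness (CRT) increase of at least 50 microns or a loss of best-corrected visual acuity (BCVA) of 5 letters or more". Methodology gives the same rule, with "a loss of best-corrected visual acuity (BCVA) of ≥ 5 letters" as its second limb, and the Pre-specified clinical outcome under Eligibility repeats it.

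**Collection.** The Study Schedule Table enters "BCVA (Optional" at each of Visits 1 to 12. OCT and plain VA stand at the same 12 visits without that label. Study Design says: "Both arms will attend monthly clinic visits for standard evaluations, including VA, BCVA, and OCT". The first secondary objective is to "Correlate CRYSTALSIGHT scores with BCVA and OCT findings".

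**Scoring.** In the Sample size calculation, a home result is correct when it matches the OCT findings. A participant's accuracy is the number of correct results over the number of clinic visits. The control arm is likewise judged by Amsler Grid and OCT. This measure carries the 0.09 margin. Elsewhere, Study Design has progression "determined by the investigator, based on standardised OCT confirmation", and the Figure 6 caption requires OCT confirmation for the confusion matrix.

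**Rank.** Study Design says: "The second aim will be to compare the accuracy of CRYSTALSIGHT and Amsler".

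**The concern.** There are two separate problems.

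The first is collection. One limb of the recurrence definition needs a best-corrected acuity at baseline (the natural reference, although none is named) and at later visits. The schedule requires neither, and another section of the same document says BCVA is done monthly. A site that follows the schedule complies with it and may still leave the BCVA limb unassessable.

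The second is scoring. CRT is read from OCT; BCVA is not. An endpoint scored on OCT alone cannot register a recurrence that shows only in acuity. The stated objective and the one comparison with a margin therefore use different reference standards. At stake is whether a non-inferiority result on accuracy would answer the question in the Primary Objective.

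**Working it through.** **1. Which endpoint N rests on.** Inputs from the Sample size calculation: margin 0.09, SD 0.21, one-sided alpha 0.025, power 0.80, accuracy 0.80 in both arms (true difference 0), dropout 21%. For a non-inferiority test of two means:

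n per arm = 2 x SD² x (z₀.₉₇₅ + z₀.₈₀)² / margin² = 2 x 0.21² x (1.960 + 0.842)² / 0.09² = 85.5, so 86.

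With the t distribution it is 87. Then 2 x 87 / 0.79 = 220.3, which agrees with the planned 220. The global sample size is thus built on OCT-scored accuracy.

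**2. Schedule count.** BCVA is optional at 12 of 12 visits. OCT is unconditional at 12 of 12, and so is VA. VA is listed separately from BCVA, is not said to be best-corrected, and is nowhere allowed to stand in for it. Methodology does look for earlier detection "as reflected by better VA and CRT values at the time of detection", but that concerns VA and is not the recurrence rule.

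**3. The two standards side by side.**

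| Visit | Recurrence under the objective | Recurrence under the accuracy rule | Alert / no alert scored as |
|---|---|---|---|
| CRT up 50 microns or more, OCT read as recurrence | yes | yes | correct / wrong |
| BCVA down 5 letters or more, OCT read as no recurrence | yes | no | wrong / correct |
| BCVA down 5 letters or more, CRT rise under 50 microns, fluid or CNV on OCT | yes | not fixed | not fixed |
| BCVA loss under 5 letters, CRT rise under 50 microns, fluid or CNV on OCT | no | not fixed | not fixed |

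Row 2 is the contradiction. Rows 3 and 4 are open because the accuracy rule names no OCT criterion, while inclusion criterion 5 describes recurrence by CNV or by intraretinal or subretinal fluid.

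**4. What row 2 can do.** Let f be the share of scored visits in row 2 and a the probability of an alert at such a visit. Against the definition these visits contribute f x a to accuracy; against OCT they contribute f x (1 - a). The change is f x (1 - 2a).

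- Level in one arm: with a = 0.80 the change is -0.6f. The documents give no f. Purely as an assumption, recurrence at 5% to 30% of visits, with 10% to 50% of those in row 2, gives f = 0.005 to 0.15. An accuracy of 0.80 would then read 0.797 to 0.710.
- Difference between arms: with equal f and equal a the changes cancel. With equal f and alert probabilities differing by d, the difference shifts by 2 x f x d against the more sensitive method. For example, f = 0.05 and d = 0.30 (both assumed) give 2 x 0.05 x 0.30 = 0.03.

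**The case against.** **The accuracy rule does not say that OCT is negative whenever CRT has risen by less than 50 microns.** This stands. A reader might infer that every recurrence meeting only the BCVA limb is scored backwards. The text does not support that: a visit with acuity loss and fluid on OCT could well be read as OCT-positive, and an alert there would be correct. Reversal is certain only where OCT is read as showing no recurrence.

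**No bias in the comparison has been shown.** This also stands. Both arms are scored against OCT, and the frequency of the discordant visits is unknown. A reader might set one visit's weight in a participant's accuracy (1/12 = 0.083) beside the 0.09 margin, but the first is a step in one person's score and the second a difference in arm means. Nor do the documents support a claim that the SD would change in a known direction.

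**The two harms are alternatives.** This stands in part. If Study Design governs, BCVA is measured monthly; if OCT governs, accuracy is computable at every scheduled visit. In both cases the objective and the scored endpoint still differ.

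**The working text already leans on OCT.** True. Event confirmation, the confusion matrix, the scoring rule and the Cohort 1 threshold work all rest on it. This is a good reason not to favour scoring on the composite. It does not justify leaving the objective on a different definition.

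**The SAP can settle it.** It could define a positive OCT or a reference visit for BCVA loss. It cannot recover a BCVA that was never taken, and the two statements on BCVA conflict within the Protocol itself.

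**Conclusion.** The point holds in this form. The Protocol contradicts itself on whether BCVA is required, and following the schedule can leave one limb of the recurrence definition unassessed. Accuracy, the only measure with a non-inferiority margin, uses a reference standard that differs from the objective's. For visits with a BCVA loss of at least 5 letters and an OCT scan read as negative, the scoring runs opposite to the objective. For visits with fluid or CNV but a CRT rise under 50 microns, the scoring is undetermined.

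The size of the effect on the result cannot be derived from the documents, and the figures in step 4 of the working are illustrations under assumed frequencies. No shift in the arm difference is claimed; one arises only if the discordant visits, or their detection, differ by arm. The conclusion takes the accuracy rule at its natural meaning, that a result disagreeing with OCT is incorrect. The matter needs correcting in the Protocol because an acuity not measured at a visit cannot be obtained later.

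**What to change.** 1. **Collection.** Delete the optional label after BCVA at baseline and every scheduled visit. This matches Study Design and serves the first secondary objective. Cost: at most 12 x 220 = 2,640 scheduled assessments, fewer with early exit or dropout.

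2. **One reference standard** for the objective and the accuracy measure, by either route (not ranked):
   - (a) Score home results in both arms against the full CRT-or-BCVA definition, and record BCVA at every scored visit, including triggered ones. Cost: the extra triggered-visit assessments, and a recheck of the 0.80 accuracy, the SDs (0.12 and 0.21) and the 0.09 margin, which were set for OCT scoring. The global plan leaves little room: 110 x 0.79 = 86.9 evaluable per arm against 87 needed.
   - (b) Restate the Primary Objective, Methodology and Pre-specified clinical outcome on one explicit OCT/CRT criterion, use the same criterion in the accuracy rule, and keep BCVA as a secondary measure. Cost: an amendment to the primary outcome.

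3. **Rank.** State whether accuracy is the primary endpoint or the second aim named in Study Design.

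The OCT-confirmation wording in Study Design, the exit wording in the Figure 5 caption and the description of recurrence in inclusion criterion 5 must be reconciled with whichever standard is chosen. No clinical rule is proposed here.
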